## **8.10. Data Monitoring Committee**

An external data monitoring committee (DMC) comprised of an independent statistician and two independent gastroenterologists will review the progress of the study and perform interim reviews of safety data and provide recommendation to Gilead whether the nature, frequency, and severity of adverse effects associated with study treatment warrant the early termination of the study in the best interests of the participants, whether the study should continue as planned, or the study should continue with modifications.

The DMC will meet twice to evaluate all available safety data from the study. The initial meeting will occur after approximately 20% of the planned total number of subjects reach the Week 10 visit. Following this, the next meeting will occur after approximately 50% of the subjects reach the Week 10 visit. Additional DMC meetings may be convened, if needed.

An ad hoc convening of the DMC may be triggered by the following conditions:

≥ 2 subjects develop the same (by PT) related, Grade 4, unexpected AE in the infections and infestations SOC

≥ 2 subjects develop any related, Grade 4, thromboembolic events that have been positively adjudicated by the adjudication committee (see Section [8.11](#))

Any subject develops a Grade 5, related, unexpected AE. The definition of an unexpected AE will be based on the reference safety information that is on file at the time the event occurs

The DMC's specific activities will be defined by a mutually agreed upon charter, which will define the DMC's membership, conduct, and meeting schedule.

While the DMC will be asked to advise Gilead regarding future conduct of the study, including possible early study termination, Gilead retains final decision-making authority on all aspects of the study. If the DMC recommends stopping the study for lack of efficacy, a Gilead executive team will be unblinded to confirm the DMC recommendation.

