the United States will be limited to subjects who have failed at least 2 biologic therapies (any TNF $\alpha$  antagonists and vedolizumab). Refer to the IB for further information about nonclinical testicular findings.

Administration of filgotinib produces an increase in embryofetal malformations in pregnant rats and rabbits at exposures similar to, or slightly higher than, exposures associated with a 200 mg once daily dose in CD subjects; the use of highly effective contraception in the subject population is expected to mitigate this risk.

JAK inhibition is expected to increase the risk of infection based on mechanism of action. Across global studies with filgotinib, in general, active treatment arms have increased incidences of infection versus placebo. In the present protocol, treatment interruption and discontinuation considerations surrounding infections are incorporated and sites and investigators will be trained regarding such circumstances. All subjects will be screened for tuberculosis (TB) and subjects with active infections will be excluded. Malignancy has been reported in subjects on filgotinib; in the present trial, subjects will be required to have up to date colorectal cancer screening and surveillance and subjects with recent malignancies will be excluded as outlined in the eligibility criteria. For further details about infections and malignancies, please reference the IB.

The potential benefits of JAK inhibition include improvement in clinical symptoms and mucosal and endoscopic healing. JAK inhibition may be efficacious in the treatment of IBD based on results from FITZROY. A lack of response contingency after Week 10 will enable early access to active drug when clinically indicated. In FITZROY, an increase in mean hemoglobin concentration was observed, without difference between filgotinib and placebo. No clinically significant changes from baseline in mean neutrophil counts or liver function tests were observed at 10 weeks. Filgotinib treated subjects showed an increase in HDL and no significant change in LDL. Lipid and hemoglobin effects represent potential benefits in this population.

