## 7.2.2. Assessment of Severity

The severity of AEs will be graded using the modified Common Terminology Criteria for Adverse Events (CTCAE), version 4.03. For each episode, the highest grade attained should be reported.

If a CTCAE criterion does not exist, the investigator should use the grade or adjectives: Grade 1 (mild), Grade 2 (moderate), Grade 3 (severe), Grade 4 (life-threatening) or Grade 5 (fatal) to describe the maximum intensity of the AE. For purposes of consistency with the CTCAE, these intensity grades are defined in [Table 7-1](#) and [Appendix 6](#).

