**Table 7-1. Grading of Adverse Event Severity**

| Grade   | Adjective        | Description   |
|---------|------------------|---|
| Grade 1 | Mild             | Asymptomatic or mild symptoms; clinical or diagnostic observations only; intervention not indicated   |
| Grade 2 | Moderate         | Local or noninvasive intervention indicated; limiting age-appropriate instrumental ADL  |
| Grade 3 | Severe           | Severe or medically significant but not immediately life-threatening; hospitalization or prolongation of hospitalization indicated; disabling; limiting self-care ADL |
| Grade 4 | Life-threatening | Urgent intervention indicated   |
| Grade 5 | Death            | Death related AE  |

\* Activities of Daily Living (ADL) Instrumental ADL refer to opening preparing meals, shopping for groceries or clothes, using the telephone, managing money, etc.

\*\* Self care ADL refer to bathing, dressing and undressing, feeding self, using the toilet, taking medications, and not bedridden

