#### **7.4. Gilead Reporting Requirements**

Depending on relevant local legislation or regulations, including the applicable US FDA Code of Federal Regulations (CFR), the EU Clinical Trials Directive (2001/20/EC) and relevant updates, and other country-specific legislation or regulations, Gilead may be required to expedite to worldwide regulatory agencies reports of SAEs, serious adverse drug reactions (SADRs), or SUSARs. In accordance with the EU Clinical Trials Directive (2001/20/EC), Gilead or a specified designee will notify worldwide regulatory agencies and the relevant IEC in concerned Member States of applicable SUSARs as outlined in current regulations.

Assessment of expectedness for SAEs will be determined by Gilead using reference safety information specified in the IB or relevant local label as applicable.

All investigators will receive a safety letter notifying them of relevant SUSAR reports associated with any study IMP. The investigator should notify the IRB or IEC of SUSAR reports as soon as is practical, where this is required by local regulatory agencies, and in accordance with the local institutional policy.

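### A fatal thromboembolic event classed as expected falls under none of the ad hoc DMC triggers, although two Grade 4 events of the same kind would meet one

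*Protocol*

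**What the plan says.** Protocol 8.10 names three conditions for an ad hoc DMC meeting.

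- Infection trigger: at least "2 subjects develop the same (by PT) related, Grade 4, unexpected AE in the infections and infestations SOC".
- Thromboembolism trigger: at least "2 subjects develop any related, Grade 4, thromboembolic events that have been positively adjudicated by the adjudication committee". Expectedness plays no part.
- Fatal-event trigger, any organ class: "Any subject develops a Grade 5, related, unexpected AE".

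On expectedness, the same section states: "The definition of an unexpected AE will be based on the reference safety information that is on file at the time the event occurs". Protocol 7.4 gives the assessment for serious events to the sponsor: "Assessment of expectedness for SAEs will be determined by Gilead using reference safety information specified in the IB".

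On grading, Protocol 7.2.2 states: "For each episode, the highest grade attained should be reported". Table 7-1 describes Grade 5 as "Death related AE".

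Section 8.10 schedules two DMC meetings, when about 20% and about 50% of subjects have reached Week 10. It allows further meetings if needed and says that the listed conditions may, not must, lead to an ad hoc meeting.

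**The concern.** The thromboembolism trigger names Grade 4 with no upward range. Because each episode carries only its highest grade, a fatal embolism is a Grade 5 event and not also a Grade 4 event. It drops out of the count of two and has to be caught by the fatal-event trigger, which adds a condition that the thromboembolism trigger does not have: the event must be unexpected.

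The thromboembolism trigger is the only one of the three without that condition, so as drafted it asks for review of these events whether or not they are listed. The fatal-event trigger brings the condition back for the worst outcome. For expected events the ordering is inverted: two survivors meet a trigger and two deaths do not. The documents give no reason for this.

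At stake is the rule-based route to DMC review between and after the scheduled meetings. When the second meeting falls due, about half of the 100 planned subjects have still to reach Week 10, and treatment runs to Week 24.

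**Working it through.** The plan gives no figure on this point to reproduce, so the check is a truth table of the three triggers, followed by an illustration under assumed rates.

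**Inputs.** The trigger wording and the basis for expectedness come from Protocol 8.10. The rule that one episode carries one grade, the highest, comes from Protocol 7.2.2, and the meaning of Grade 5 from Table 7-1.

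**Step 1: the triggers as conditions.** Take every event as related. Take thromboembolic events as positively adjudicated and infections as sharing one preferred term. Let n4 and n5 be the numbers of subjects with a Grade 4 and a Grade 5 event.

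- Infection trigger: n4 (unexpected only) ≥ 2
- Thromboembolism trigger: n4 (expected or not) ≥ 2
- Fatal-event trigger: n5 (unexpected only) ≥ 1

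**Step 2: is any trigger met?**

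| Events | one G4 | one G5 | G4 + G4 | G4 + G5 | G5 + G5 |
|---|---|---|---|---|---|
| Infection, unexpected | no | yes (fatal) | yes (infection) | yes (fatal) | yes (fatal) |
| Infection, expected | no | no | no | no | no |
| Thromboembolism, unexpected | no | yes (fatal) | yes (thromboembolism) | yes (fatal) | yes (fatal) |
| Thromboembolism, expected | no | no | **yes (thromboembolism)** | **no** | **no** |

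Only the last row is inverted. In both unexpected rows a single death is enough, where two Grade 4 events are needed. In the expected-infection row, neither grade counts.

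**Step 3: the effect of the change.** With *Grade 4 or higher*, the thromboembolism condition becomes n4 + n5 ≥ 2. In the last row, G4 + G5 gives 1 + 1 = 2 and G5 + G5 gives 0 + 2 = 2, so both are met. A single expected death gives 1 and is still not met, like a single Grade 4 event. The same edit to the infection trigger changes no cell of the table.

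**Step 4: illustrative size.** The documents give no event rates. Assume 100 subjects pooled over arms, per-subject risks p4 and p5 of a Grade 4 and a Grade 5 thromboembolic event, and all events related, positively adjudicated and expected. Then

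P(at least 2 of 100) = 1 − (1 − p)^100 − 100·p·(1 − p)^99,

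with p = p4 as written and p = p4 + p5 after the change. For p = 0.01 this is 1 − 0.366 − 0.370 = 0.264.

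| Assumed p4 | Assumed p5 | As written | Grade 4 or higher |
|---|---|---|---|
| 1% | 0.2% | 0.264 | 0.338 |
| 1% | 0.5% | 0.264 | 0.443 |
| 1% | 1% | 0.264 | 0.597 |
| 2% | 0.5% | 0.597 | 0.717 |
| 2% | 1% | 0.597 | 0.805 |

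These figures show how the gap scales. They do not estimate its size in this trial.

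**The case against.** The strongest reply is that the gap may be empty. It exists only if the reference safety information on file lists a thromboembolic term, and that information is not in the documents. The risk section (Protocol 1.5) discusses testicular and embryofetal findings, infection and malignancy, but not thromboembolism. This stands as a limit on size. However, expectedness is tied to the information on file when the event occurs, so the gap could open during the trial without any protocol change.

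A second reply is that an unmet trigger blocks nothing. The triggers are permissive, and further meetings may be called if needed. Other oversight continues:

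- Serious events reach the sponsor within 24 hours (Protocol 7.3.2).
- Safety personnel may be unblinded to cases and group summaries (Protocol 5.1.2).
- All potential thromboembolic events go to adjudication (Protocol 8.11), as do all adverse events leading to death (SAP 7.1.7.1).

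This also stands, and it makes it unlikely that two such deaths would go unexamined. It does not repair a listed condition that puts deaths below survivable events. The DMC charter, which might handle this differently, is not available.

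One might also say that Grade 4 was meant to include worse. The documents state a range where they mean one, as in Protocol 7.6.2 (recurrence at Grade 3 or above) and SAP 7.1.6.1 (summaries from Grade 3 upward), so the literal reading is reasonable.

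A reader might infer that infections have the same defect, particularly as Protocol 1.5 says that "JAK inhibition is expected to increase the risk of infection based on mechanism of action". The documents do not support that. The infection trigger is itself limited to unexpected events, and one related, unexpected fatal infection already meets the fatal-event trigger, with no second subject and no shared preferred term required. Two deaths from a listed infection do meet no trigger, but neither do two Grade 4 cases of it; the expectedness condition excludes both. The Protocol 1.5 sentence concerns mechanism and does not show what the reference information lists.

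**Conclusion.** The point holds for one category: related, positively adjudicated thromboembolic events classed as expected. There, G4 + G4 meets a trigger, while G4 + G5 and G5 + G5 meet none. It does not hold for infections, nor for thromboembolic deaths that are unexpected.

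The conclusion rests on reading Grade 4 literally and on each episode carrying only its highest grade. The practical size is unknown and could be zero, because the reference safety information is not available. Under the assumed rates above, the chance of meeting the trigger rises from 0.264 to between 0.338 and 0.597 for a 1% Grade 4 risk, and from 0.597 to between 0.717 and 0.805 for a 2% Grade 4 risk.

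It would go too far to conclude that the DMC could not meet after such deaths, or that fatal events in general count for less than life-threatening ones. This is a drafting gap in a safety rule, limited in consequence and worth closing because closing it takes so little.

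**What to change.** In the thromboembolism trigger of Protocol 8.10, change *Grade 4* to *Grade 4 or higher*. Make the same change in the DMC charter if it repeats the trigger. This needs a few words in an amendment and no extra data collection. The downside is possibly one more ad hoc DMC meeting.

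Nothing else is needed for this point. The infection trigger, its same-preferred-term condition and the fatal-event trigger can stay as they are; changing them would be a separate choice about criteria on which the documents do not contradict themselves.

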## **8.11. Cardiovascular Safety Endpoint Adjudication Committee (CVEAC)**

An independent adjudication committee will be formed to periodically review and adjudicate all potential major adverse cardiovascular events and thromboembolic events in a blinded manner.

The CVEAC's specific activities will be governed by a mutually agreed charter, which will define the CVEAC's membership, conduct, and meeting schedule.

The following events will be adjudicated and classified by the CVEAC:

- Cardiovascular death
- Myocardial infarction
- Stroke
- Arterial thromboembolism
- Venous thromboembolism (eg, deep venous thrombosis, pulmonary embolism)

Further details will be specified in the CVEAC charter.

## **9. RESPONSIBILITIES**

### **9.1. Investigator Responsibilities**

#### **9.1.1. Good Clinical Practice**

The investigator will ensure that this study is conducted in accordance with the principles of the Declaration of Helsinki, International Council for Harmonisation (ICH) guidelines, or with the laws and regulations of the country in which the research is conducted, whichever affords the greater protection to the study subject. These standards are consistent with the European Union Clinical Trials Directive 2001/20/EC and Good Clinical Practice Directive 2005/28/EC.

The investigator will ensure adherence to the basic principles of Good Clinical Practice, as outlined in 21 CFR 312, subpart D, "Responsibilities of Sponsors and Investigators," 21 CFR, part 50, and 21 CFR, part 56.

The investigator and all applicable subinvestigators will comply with 21 CFR, Part 54, providing documentation of their financial interest or arrangements with Gilead, or proprietary interests in the investigational drug under study. This documentation must be provided prior to the investigator's (and any subinvestigator's) participation in the study. The investigator and subinvestigator agree to notify Gilead of any change in reportable interests during the study and for 1 year following completion of the study. Study completion is defined as the date when the last subject completes the protocol-defined activities.

#### **9.1.2. Institutional Review Board (IRB)/Independent Ethics Committee (IEC) Review and Approval**

The investigator (or sponsor as appropriate according to local regulations) will submit this protocol, ICF, and any accompanying material to be provided to the subject (such as advertisements, subject information sheets, or descriptions of the study used to obtain informed consent) to an IRB/IEC. The investigator will not begin any study subject activities until approval from the IRB/IEC has been documented and provided as a letter to the investigator.

Before implementation, the investigator will submit to and receive documented approval from the IRB/IEC any modifications made to the protocol or any accompanying material to be provided to the subject after initial IRB/IEC approval, with the exception of those necessary to reduce immediate risk to study subjects.

#### **9.1.3. Informed Consent**

The investigator is responsible for obtaining written informed consent from each individual participating in this study after adequate explanation of the aims, methods, objectives, and potential hazards of the study and before undertaking any study-related procedures. The study investigator must ensure that the potential risk of infertility is discussed with all male subjects during the informed consent process. The investigator must use the most current IRB/IEC

approved consent form for documenting written informed consent. Each informed consent (or assent as applicable) will be appropriately signed and dated by the subject or the subject's legally authorized representative and the person conducting the consent discussion, and also by an impartial witness if required by IRB/IEC or local requirements. The consent form will inform subjects about genomic testing and sample retention.

#### **9.1.4. Confidentiality**

The investigator must assure that subjects' anonymity will be strictly maintained and that their identities are protected from unauthorized parties. Only subject initials, date of birth, another unique identifier (as allowed by local law) and an identification code will be recorded on any form or biological sample submitted to the Sponsor, IRB/IEC, or laboratory. Laboratory specimens must be labeled in such a way as to protect subject identity while allowing the results to be recorded to the proper subject. Refer to specific laboratory instructions or in accordance with local regulations. NOTE: The investigator must keep a screening log showing codes and names for all subjects screened and for all subjects enrolled in the trial. Subject data will be processed in accordance with all applicable regulations.

The investigator agrees that all information received from Gilead, including but not limited to the IB, this protocol, eCRF, the IMP, and any other study information, remain the sole and exclusive property of Gilead during the conduct of the study and thereafter. This information is not to be disclosed to any third party (except employees or agents directly involved in the conduct of the study or as required by law) without prior written consent from Gilead. The investigator further agrees to take all reasonable precautions to prevent the disclosure by any employee or agent of the study site to any third party or otherwise into the public domain.

#### **9.1.5. Study Files and Retention of Records**

The investigator must maintain adequate and accurate records to enable the conduct of the study to be fully documented and the study data to be subsequently verified. These documents should be classified into at least the following two categories: (1) investigator's study file, and (2) subject clinical source documents.

The investigator's study file will contain the protocol/amendments, CRF and query forms, IRB/IEC and governmental approval with correspondence, informed consent, drug records, staff curriculum vitae and authorization forms, and other appropriate documents and correspondence.

The required source data should include sequential notes containing at least the following information for each subject:

- Subject identification (name, date of birth, gender);
- Documentation that subject meets eligibility criteria, ie, history, PE, and confirmation of diagnosis (to support inclusion and exclusion criteria);
- Documentation of the reason(s) a consented subject is not enrolled

- Participation in study (including study number);
- Study discussed and date of informed consent;
- Dates of all visits;
- Documentation that protocol specific procedures were performed;
- Results of efficacy parameters, as required by the protocol;
- Start and end date (including dose regimen) of IMP, including dates of dispensing and return;
- Record of all AEs and other safety parameters (start and end date, and including causality and severity);
- Concomitant medication (including start and end date, dose if relevant; dose changes);
- Date of study completion and reason for early discontinuation, if it occurs.

All clinical study documents must be retained by the investigator until at least 2 years or according to local laws, whichever is longer, after the last approval of a marketing application in an ICH region (ie, United States, Europe, or Japan) and until there are no pending or planned marketing applications in an ICH region; or, if no application is filed or if the application is not approved for such indication, until 2 years after the investigation is discontinued and regulatory authorities have been notified. Investigators may be required to retain documents longer if specified by regulatory requirements, by local regulations, or by an agreement with Gilead. The investigator must notify Gilead before destroying any clinical study records.

Should the investigator wish to assign the study records to another party or move them to another location, Gilead must be notified in advance.

If the investigator cannot provide for this archiving requirement at the study site for any or all of the documents, special arrangements must be made between the investigator and Gilead to store these records securely away from the site so that they can be returned sealed to the investigator in case of an inspection. When source documents are required for the continued care of the subject, appropriate copies should be made for storage away from the site.

